11.3. Visits 3, 4, 6, and 7, Procedures

The investigator or designee will complete the following procedures at Visit 3, 4, 6, and 7:

- Patient reported outcomes. Patient-reported outcomes include: Steroid toxicity questionnaire; King's Sarcoidosis Questionnaire ([Attachment 4](#)); Fatigue Assessment Scale ([Attachment 5](#)); Patient's Global Assessment ([Attachment 6](#)); Medical Research Council Dyspnea Scale ([Attachment 8](#)); Leicester Cough Questionnaire ([Attachment 9](#)), WPAI ([Attachment 10](#)).
- Vital sign determinations. Vital signs will be obtained after the subject has been seated for 5 minutes (minimum) and will include systolic and diastolic blood pressures, pulse rate, and respiratory rate (see [Section 14.4](#)).
- Weight determination. Every effort should be made for weight to be measured by the same calibrated scale at every visit.
- Physical examination (see [Section 14.3](#)). Full physical examination will include targeted examination per organ involved. All efforts must be undertaken for the same physician to perform the physical examination per subject, per organ involved at each visit.
- ePOST: All efforts must be undertaken for the same physician to perform the ePOST ([Attachment 3](#)) side-by-side with prior evaluations.
- Physician Global Assessment ([Attachment 7](#)).
- Clinical laboratory tests:
 - Complete blood count.
 - Clinical chemistry, including liver function tests. Samples will be collected from subjects who have been fasted for at least 12 hours.
 - HbA1C.
 - Human chorionic hormone (urine pregnancy testing, females of child bearing potential only – local laboratory).

- Subject diary review.
- Study drug accountability.
- Corticosteroid tapering. (At Visit 3, if the subject improved or was stable at both Visit 2 and Visit 3, tapering can be applied).
- AEs and concomitant medications.
- Contact IXRS and dispense IMP kits and encourage compliance.
- Remind the subjects to arrive in fasting condition (drinking water is permitted) for Visits 4, 5, 6, and 7 and to bring all IMP kits including used and unused vials to each visit in a cooler.

11.4. Visit 5 Procedures

In addition to all procedures described in [Section 11.3](#) the following will also be performed at Visit 5 by the investigator or designee:

- C-reactive protein.
- 25-Hydroxy vitamin D, 1, 25-dihydroxy vitamin D, parathyroid hormone (Visit 5 only).
- Urinary analysis (local laboratory).
- Subject diary review.
- Study drug accountability.
- Biomarkers sample collection (including RNA, if genetic ICF signed).
- PFT.

11.5. Visit 8 Procedures

The investigator or designee will complete the following procedures at Visit 8:

- Patient reported outcomes. Patient-reported outcomes include: Steroid toxicity questionnaire; King's Sarcoidosis Questionnaire ([Attachment 4](#)); Fatigue Assessment Scale ([Attachment 5](#)); Patient's Global Assessment ([Attachment 6](#)); Medical Research Council Dyspnea Scale ([Attachment 8](#)); Leicester Cough Questionnaire ([Attachment 9](#)), WPAI ([Attachment 10](#)).
- Vital sign determinations Vital signs will be obtained after the subject has been seated for 5 minutes (minimum) and will include systolic and diastolic blood pressures, pulse rate, and respiratory rate (see [Section 14.4](#)).
- Weight measured. Every effort should be made for weight to be measured by the same calibrated scale at every visit.
- Physical examination (see [Section 14.3](#)). The full physical examination will include a targeted examination of the organ involved. All efforts must be undertaken for the same physician to perform the physical examination, per subject, per organ involved, at each visit.

- Physician Global Assessment ([Attachment 7](#)).
- ePOST: All efforts must be undertaken for the same physician to perform the ePOST ([Attachment 3](#)) side-by-side with prior evaluations.
- 12-Lead ECG (see [Section 14.6](#)).
- PFT ([Section 7.2.2](#)).
- CXR and HRCT. Both CXR and HRCT should be evaluated side by side by investigator/radiologist for determining if the condition is improving, stable, or deteriorating based on a 5-point Likert score ([Section 7.2.3](#)).
- 6MWT: The 6MWT ([Section 7.2.12](#)) would be performed according to the ATS protocol ([Attachment 12](#)). Reasons for not performing the 6MWT will be captured in eCRF.
- Clinical laboratory tests:
 - Complete blood count.
 - Clinical chemistry (including liver function tests, samples will be collected from subjects who have been fasted for at least 12 hours, drinking water is permitted).
 - HbA1C.
 - Lipid profile.
 - C-reactive protein.
 - 25-Hydroxy vitamin D and 1, 25-dihydroxy vitamin D, and parathyroid hormone.
 - Biomarkers (including RNA, if genetic ICF signed).
 - Human chorionic hormone (urine pregnancy testing, females of child bearing potential only- local laboratory).
 - Urine analysis (local laboratory).
- Subject diary review.
- Study drug accountability.
- AEs and concomitant medications.
- Both the investigator and the subjects will independently be asked if they would choose to continue treatment. The investigator must respond before seeing the subject's response. Subjects may continue to the optional Open-label Extension Phase irrespective of their response (eg, placebo treated) at the discretion of the principal investigator.
- Subjects declining participation or ineligible (at the discretion of the principal investigator) for the Open-label Extension Phase will have end-of-treatment procedures completed (eg, return or study drug and equipment).
- Contact IXRS.

- For subjects entering the Open-Label Extension Period:
 - Remind the subjects to arrive in fasting condition for Visit 9 (drinking water is permitted) and to bring all IMP kits including used and unused vials to each visit in a cooler.
 - Dispense IMP kits and equipment.
 - Administer Acthar Gel under supervision of study staff and observation for at least 1 hour thereafter.
 - Instruct the subject to inject Acthar Gel 80 U (1 mL) 2×/week unless the subject had a single reduction of dose, in which case only 40 U (0.5 mL) 2×/week will be injected for the remainder of the study.
 - Corticosteroid tapering.

11.6. Visit 9 Procedures, Open-Label Extension Period

The investigator or designee will complete the following procedures at Visit 9:

- Patient reported outcomes. Patient-reported outcomes include: Steroid toxicity questionnaire; King's Sarcoidosis Questionnaire ([Attachment 4](#)); Fatigue Assessment Scale ([Attachment 5](#)); Patient's Global Assessment ([Attachment 6](#)); Medical Research Council Dyspnea Scale ([Attachment 8](#)); Leicester Cough Questionnaire ([Attachment 9](#)), WPAI ([Attachment 10](#)).
- Vital sign determinations Vital signs will be obtained after the subject has been seated for 5 minutes (minimum) and will include systolic and diastolic blood pressures, pulse rate, and respiratory rate (see [Section 14.4](#)).
- Weight determination. Every effort should be made for weight to be measured by the same calibrated scale at every visit.
- Physical examination (see [Section 14.3](#)). Full physical examination will include targeted examination per organ involved. All efforts must be undertaken for the same physician to perform the physical examination per subject, per organ involved at each visit.
- Physician Global Assessment ([Attachment 7](#)).
- ePOST: All efforts must be undertaken for the same physician to perform the ePOST ([Attachment 3](#)) side-by-side with prior evaluations.
- Clinical laboratory tests:
 - Complete blood count.
 - Clinical chemistry, including liver function tests. Samples will be collected from subjects who have been fasted for at least 12 hours.
 - HbA1C.
 - Human chorionic hormone (urine pregnancy testing, females of child bearing potential only- Local laboratory).

- Subject diary review.
- Study drug accountability.
- Corticosteroid tapering.
- AEs and concomitant medications.
- Contact IXRS, dispense IMP kits, and encourage compliance.
- Remind the subjects to arrive in fasting condition for Visit 10 (drinking water is permitted) and to bring all IMP kits including used and unused vials to each visit in a cooler.

11.7. Visit 10 Procedures, Open-Label Extension Period

The investigator or designee will complete the following procedures at Visit 10:

- Patient reported outcomes and assessments. Patient-reported outcomes include: Steroid toxicity questionnaire; King's Sarcoidosis Questionnaire ([Attachment 4](#)); Fatigue Assessment Scale ([Attachment 5](#)); Patient's Global Assessment ([Attachment 6](#)); Medical Research Council Dyspnea Scale ([Attachment 8](#)); Leicester Cough Questionnaire ([Attachment 9](#)), WPAI ([Attachment 10](#)).
- Vital sign determinations (see [Section 14.4](#)).
- Weight measured. Every effort should be made for weight to be measured by the same calibrated scale at every visit.
- Physical examination (see [Section 14.3](#)). The physical examination will include a targeted examination of the organ involved. All efforts must be undertaken for the same physician to perform the physical examination (per organ involved) at each visit.
- Physician Global Assessment ([Attachment 7](#)).
- ePost: All efforts must be undertaken for the same physician to perform the ePOST ([Attachment 3](#)) side-by-side with prior evaluations.
- Clinical laboratory tests:
 - Complete blood count.
 - Clinical chemistry (including liver function tests, samples will be collected from subjects who have been fasted for at least 12 hours, drinking water is permitted).
 - HbA1C.
 - 25-Hydroxy vitamin D and 1, 25-dihydroxy vitamin D, and parathyroid hormone.
 - C-reactive protein.
 - Biomarkers (including RNA, if genetic ICF signed).

- Human chorionic hormone (urine pregnancy testing, females of child bearing potential only- Local laboratory).
- Urine analysis (local laboratory).
- Subject diary review.
- Study drug accountability.
- PFT ([Section 7.2.2](#)).
- Corticosteroid tapering.
- AEs and concomitant medications.
- Contact IXRS, dispense IMP kits, and encourage compliance.
- Remind the subjects to arrive in fasting condition (drinking water is permitted) for Visit 11 and to bring all IMP kits including used and unused vials to each visit in a cooler.

11.8. Visit 11 Procedures, Open-Label Extension Period

The investigator or designee will complete the following procedures at Visit 11:

- Patient reported outcomes and assessments. Patient-reported outcomes include: Steroid toxicity questionnaire; King's Sarcoidosis Questionnaire ([Attachment 4](#)); Fatigue Assessment Scale ([Attachment 5](#)); Patient's Global Assessment ([Attachment 6](#)); Medical Research Council Dyspnea Scale ([Attachment 8](#)); Leicester Cough Questionnaire ([Attachment 9](#)), WPAI ([Attachment 10](#)).
- Vital sign determinations (see [Section 14.4](#)).
- Weight measured. Every effort should be made for weight to be measured by the same calibrated scale at every visit.
- Physical examination (see [Section 14.3](#)). The physical examination will include a targeted examination of the organ involved. All efforts must be undertaken for the same physician to perform the physical examination (per organ involved) at each visit.
- Physician Global Assessment ([Attachment 7](#)).
- ePOST: All efforts must be undertaken for the same physician to perform the ePOST ([Attachment 3](#)) side-by-side with prior evaluations.
- 12-Lead ECG (see [Section 14.6](#)).
- PFT ([Section 7.2.2](#)).
- CXR and HRCT. Both CXR and HRCT should be evaluated side by side by investigator/radiologist for determining if the condition is improving, stable, or deteriorating based on a 5-point Likert score ([Section 7.2.3](#)).
- 6MWT. The 6MWT ([Section 7.2.12](#)) would be performed according to the ATS protocol ([Attachment 12](#)). Reasons for not performing the 6MWT will be captured in eCRF.

- Clinical laboratory tests:
 - Complete blood count.
 - Clinical chemistry (including liver function tests, samples will be collected from subjects who have been fasted for at least 12 hours).
 - HbA1C.
 - Lipid profile.
 - C-reactive protein.
 - 25-Hydroxy vitamin D and 1, 25-dihydroxy vitamin D, and parathyroid hormone.
 - Biomarkers (including RNA, if genetic ICF signed).
 - Human chorionic hormone (urine pregnancy testing, females of child bearing potential only, local laboratory).
 - Urine analysis (local laboratory).
- Subject diary review.
- Study drug accountability.
- AEs and concomitant medications.
- Both the investigator and the subjects will be independently asked if they would choose to continue treatment.

Used and unused medication and study supplies will be collected from the subjects and all other end-of-treatment procedures will be performed.

11.9. Visit 12 Procedures, Follow-up Visit

The following procedures will be completed at the follow-up visit 4 weeks (± 2) days after the final dose of IMP has been administered, regardless of treatment group, and/or participation in the optional open label extension:

- Physical examination (see [Section 14.3](#)). The physical examination will include a targeted examination of the organ involved. All efforts must be undertaken for the same physician to perform the physical examination (per organ involved) at each visit.
- Vital sign determinations (see [Section 14.4](#)).
- Weight measured. Every effort should be made for weight to be measured by the same calibrated scale at every visit.
- Clinical laboratory tests:
 - Complete blood count.
 - Clinical chemistry (including liver function tests, samples will be collected from subjects who have been fasted for at least 12 hours).

- Human chorionic hormone (urine pregnancy testing, females of child bearing potential only, local laboratory).
- Urine analysis (local laboratory).
- AEs and concomitant medications.

11.10. Early Termination Procedures

Subjects who discontinue participation for any reason prior to Visit 8 or Visit 11 will have the procedures listed for Visit 8 completed as soon as possible. The reason for discontinuation should be documented in eCRF. Unused medication and study supplies will be collected from the subjects. Subjects should also return to complete the follow-up procedures during Visit 12.

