14.5. Clinical Laboratory Tests

The clinical laboratory tests are listed in [Attachment 1](#). Tests should be conducted as described in the Schedule of Study Events ([Table 1](#)). All clinical laboratory tests will be done at a central laboratory facility except for urine analysis, and urine pregnancy test which will be performed at the local laboratory. Specific instructions for collection, processing, storage, and shipment of clinical laboratory samples will be provided in a separate laboratory manual, where appropriate.

Samples for serum chemistry testing for all visits will be collected under fasting conditions (at least 12 hours, drinking water is permitted). The date and time of the sample collection must be documented on the laboratory report. Investigators must review and sign laboratory reports. The clinical significance of each laboratory abnormality will be documented. New clinically significant laboratory abnormalities or clinically significant changes in laboratory values will be reported as AEs, as appropriate.

In addition:

All female subjects of child bearing potential will have a serum pregnancy test at Screening (Visit 1). Urine pregnancy tests will be done at all other visits throughout the study. Results must be available prior to dosing with IMP. Subjects with positive results will be ineligible for study entry (Visit 1 or Visit 2) or immediately withdrawn from the study (Visit 3 through Visit 11) and the pregnancy reported as per [Section 16.5](#).

HBsAg and HBcAb will be performed at Screening (Visit 1). Results of these tests must be negative or nonreactive for subjects to qualify for the study.

HCV will be performed at Screening (Visit 1). A positive HCV will automatically trigger a HCV PCR analysis. HCV PCR must be < 25 IU/mL to qualify for the study.

IGRA for TB will be performed at Screening (Visit 1). Results of this test must be negative for subjects to qualify for the study.

Out-of-Range Laboratory Values

Laboratory values from samples collected at Screening (Visit 1) will be evaluated by the investigator for eligibility of the subject in the study. Clinical laboratory tests may be repeated once to determine subject eligibility.

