17. SUBJECT DISCONTINUATION OR WITHDRAWAL

17.1. Subject Withdrawal

Subjects who discontinue, or are withdrawn from the study for any reason, will be required to have the early termination safety and efficacy assessment procedures (Visit 8, see [Section 11.5](#)) as well as follow up procedures (Visit 12, see [Section 11.9](#)).

The reason for discontinuation will be recorded. A subject may be discontinued from the study for the following medical or administrative reasons:

Withdrawal by Subject

Subjects will be free to discontinue from the study at any time. Subjects who have received at least 1 dose of IMP but do not complete the study will not be replaced.

AE

If a dosed subject experiences an AE that, in the judgment of the investigator, sponsor or MM, presents an unacceptable consequence or risk to the subject, the subject will be discontinued from IMP. In addition, subjects who experience any of the AEs described in [Section 12.3.1](#) may have their dose reduced by 50% once or discontinued ([Section 17](#)).

Death

In the event that a subject dies during the study, death will be the reason for discontinuation.

Lost to Follow-up

Every effort should be made to maintain contact with subjects during their participation in the study. A subject may be considered lost to follow-up if there is no response to 3 attempts to reach the subject by telephone or electronically and no response to a certified letter sent to the last known address of the subject. Efforts to contact the subject should be noted in source documentation.

Met Withdrawal Criteria

Discontinuation from IMP is mandated if the subject becomes pregnant or receives live or live-attenuated vaccines.

Worsening of Disease Activity

Subjects may be withdrawn if, in the opinion of the investigator, there is a lack of efficacy during the study.

Other

If the above reasons are not applicable, please use the “Other” option and provide the appropriate reason for subject withdrawal.

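### As worded, the protocol requires a chest X-ray and HRCT in a subject withdrawn for a positive pregnancy test; no exemption is stated

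*Protocol*

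**What the plan says.** Four protocol sections matter.

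- **14.5, Clinical Laboratory Tests.** A subject with a positive test after randomization is "immediately withdrawn from the study (Visit 3 through Visit 11"). This is withdrawal from the study, not only from the drug. The section's one rule on when a result must be known concerns dosing: "Results must be available prior to dosing with IMP".
- **11.10, on early termination.** The rule reads: "Subjects who discontinue participation for any reason prior to Visit 8 or Visit 11 will have the procedures listed for Visit 8 completed", and this is to happen without delay.
- **17.1, Subject Withdrawal.** Subjects who leave or are withdrawn, whatever the reason, "will be required to have the early termination safety and efficacy assessment procedures", with a pointer to the Visit 8 list in 11.5. Among its listed reasons the same section states: "Discontinuation from IMP is mandated if the subject becomes pregnant or receives live or live-attenuated vaccines".
- **11.5, Visit 8 Procedures.** The list contains "CXR and HRCT. Both CXR and HRCT should be evaluated side by side by investigator/radiologist", with no condition attached. It also contains "Human chorionic hormone (urine pregnancy testing, females of child bearing potential only- local laboratory"). Section 11.8 lists the same imaging and the same local test for Visit 11.

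Section 16.5, Pregnancy Reporting, covers stopping treatment, reporting the pregnancy and following its outcome. It does not mention imaging.

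**The concern.** The early-termination rule is meant to collect a last set of safety and efficacy data from everyone who leaves. Because it brings in the whole Visit 8 list, it brings in a chest X-ray and a chest CT as well. For most subjects who leave, that is reasonable. For one withdrawn because she is pregnant, the protocol requires radiation imaging at the moment her pregnancy has been established, and it states no clinical need for the scans.

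It looks like an oversight. The protocol handles pregnancy in detail elsewhere: a serum test at screening, urine tests at later visits, a result needed before dosing, withdrawal and outcome reporting. It can also make an allowance for a single procedure, since the Visit 8 list provides for recording why a walk test was not done. Imaging has no such allowance.

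What is at stake is subject safety and clear instructions to approximately 75 sites. It is not the validity of the efficacy comparison.

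**Working it through.** The plan gives no figure to reproduce. The check is a reading of the text, plus two small counts.

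**1. The chain.**
- Positive test at Visits 3 to 11: withdrawn from the study (14.5).
- Withdrawn for whatever reason: Visit 8 procedures apply (11.10) and are required (17.1).
- Visit 8 procedures: include CXR and HRCT (11.5).

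Sections 16.5 and 17.1 speak of stopping the drug on pregnancy. That does not break the chain, because 14.5 speaks of leaving the study.

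**2. Search for an exemption.**
- 16.5: silent on imaging.
- 7.2.3 (Imaging) and schedule footnote o in Protocol Table 1, repeated in SAP 15.3: no mention of pregnancy.
- 12.3.1: asks for all efforts to complete end-of-treatment procedures, which is softer than 17.1, but only for subjects withdrawn because of an adverse event.
- 14.1: a general duty on the site to provide safety measures.
- 19: allows departures from the protocol to remove an immediate hazard.

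None of these exempts imaging in pregnancy.

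**3. Where the rule bites.** Visits at which a positive test means withdrawal: 3, 4, 5, 6, 7, 8, 9, 10 and 11, which is 9. Of these, CXR and HRCT are scheduled at Visits 8 and 11, which is 2. At 9 − 2 = 7 visits (3 to 7, 9 and 10) the scans would be done only because of the early-termination rule. This counts occasions on which the rule could apply; it does not measure risk. The documents give no pregnancy rate, so I estimate no number of subjects.

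**4. What omitting the scan would cost the analysis.** HRCT is one of six components of the Sarcoidosis Treatment Score (STS). It is done at screening and Visits 8 and 11 only. A subject withdrawn before Visit 8 without the scan has no post-baseline HRCT to carry forward. Under SAP 9.1 her Week 24 score stays missing and she counts as a non-responder. SAP 4.1 gives 55 randomized. With the 1:1 allocation I assume arms of 27 and 28:

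- 1/28 = 3.57%
- 1/27 = 3.70%
- at the planned 50 per arm, 1/50 = 2.0%

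This is the largest change one such subject can make to her arm's responder rate. It occurs only if she would have been classed as a responder with the scan; otherwise the change is zero. It also supposes that an early-termination scan would have counted towards Week 24. The efficacy set is the modified intent-to-treat population, which may be smaller than 55; one subject would then weigh slightly more.

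**The case against.** The strongest reply is that no clause was written to send a pregnant subject for imaging. The requirement appears only when four general clauses are read together, and several things stand between the wording and a scan. Subjects of childbearing potential must use contraception and are tested repeatedly. A subject may leave at any time and can decline. Section 11 expects that procedures will sometimes be missed and asks that this be recorded. Conduct is under good clinical practice. The consent form and the Study Operations Manual are not among the documents and may address imaging. The documents also give no measure of fetal risk and no pregnancy rate.

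Much of this stands, and it limits the size of the point: few subjects, and an actual scan is unlikely. It does not remove the point. Each of these provisions relies on a site or a subject not doing what 17.1 requires, and none changes the wording of 11.10 or 17.1.

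Stronger readings are tempting, and the documents do not support them.

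- **That subjects are sent for scans before the same-visit pregnancy test is read.** The only timing rule in 14.5 concerns dosing, so that order is permitted, but nothing directs it. The urine tests at Visits 8 and 11 are local (for Visit 11: "Human chorionic hormone (urine pregnancy testing, females of child bearing potential only, local laboratory")), and a site is free to read them first. This is silence about order within a visit, not an error.
- **That screening scans should wait for the serum result at no cost.** That test goes to the central laboratory, while 11.1 lists imaging at the same screening visit. Waiting could mean a separate attendance for imaging, even though the 28-day window leaves room for one.
- **That the exemption would cost a Week 48 score.** For a withdrawal at Visit 9 or 10, the SAP applies no imputation in the extension and states no rule mapping early-termination data to Visit 11. Her Week 48 score would be missing with or without the scan, so I do not count it.

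**Conclusion.** The point holds in this form: read exactly, 14.5, 11.10, 17.1 and 11.5 together require a chest X-ray and an HRCT in a subject withdrawn for a positive pregnancy test, and no exemption is stated. It is a patient-safety fault in the wording and should be corrected. Each affected subject would have one CXR and one HRCT; for a withdrawal at Visit 9 or 10 this would be a third set, after screening and Visit 8.

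A reader might infer that pregnant subjects were, or would be, scanned. The documents do not show that, and the general safeguards make it unlikely. The conclusion rests on the protocol and SAP text alone and needs no assumption about pregnancy rates or radiation dose. Only the analysis cost rests on assumptions: the even split of the 55 randomized and the use of an early-termination scan at Week 24.

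**What to change.** Add to 11.10 and to 17.1: *CXR and HRCT will not be performed in subjects with a positive pregnancy test.* Cross-refer to it in 16.5, and apply the same sentence at Visits 8 and 11, where both scans are already listed. All other early-termination assessments stay as they are.

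The cost is one sentence in two places and a cross-reference, with no added test or visit. The analysis loses the end-of-treatment HRCT for the few subjects concerned. SAP 9.1 already deals with that through its non-responder rule, so the SAP needs no change.

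Optionally, and apart from the core fix, ask sites to read the local urine test before imaging at Visit 8, Visit 11 and early termination. I would not make screening scans wait for the central serum result; if the sponsor wants that, the protocol should say that it may need a separate imaging attendance.

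The SAP reports 55 randomized, and the documents do not say whether anyone is still on study. If someone is, amend the protocol or notify sites; if not, carry the sentence into the next protocol that uses this early-termination wording.
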